9.10 OTHER ASPECTS

9.10.1 Data quality assurance

A quality assurance audit/inspection of this study may be conducted by the sponsor or sponsor's designees or by Institutional Review Board (IRBs)/Independent Ethics Committee (IECs) or by regulatory authorities. The quality assurance auditor will have access to all medical records, the investigator's study-related files and correspondence, and the informed consent documentation of this study.

9.10.2 Study records

Case Report Forms (CRFs) for individual patients will be provided by the sponsor via paper. All paper CRFs should be typed or filled out with a black ball-point pen and must be legible.

- Corrections to paper forms will be made by a single line stroke through the error and insertion of the correction above or beside the error. The change must be initialed and dated by the investigator or a member of the study staff authorized by the investigator on the Authority Form. No erasers, correction fluid, or tape may be used.
- The principal investigator will sign and date the indicated places on the CRFs. These signatures will indicate that the principal investigator inspected or reviewed the data on the CRF, the data queries, and the site notifications, and agrees with the content.

9.10.2.1 Source documents

Source documents are original documents, data, and records from which the subject's CRF data are obtained. These include but are not limited to hospital records, clinical and office charts, laboratory and pharmacy records, diaries, microfiches, radiographs, and correspondence. Case report form entries may be considered source data if the CRF is the site of the original recording (i.e., there is no other written or electronic record of data).

Source documents provide evidence for the existence of the patient and substantiate the integrity of the data collected. Source documents are filed at the investigator's site.

Data reported on the CRFs that are transcribed from source documents must be consistent with the source documents or the discrepancies must be explained. The investigator may need to request previous medical records or transfer records, depending on the study; also current medical records must be available.

For paper CRFs, the following data need to be derived from source documents:

- Patient identification (gender, date of birth, etc.)
- Patient participation in the study (substance, study number, patient number, date patient was informed)
- Dates of patient's visits, including prescription of study medication
- Medical history (including concomitant diseases and concomitant, if applicable)

- Adverse drug reactions and outcome events (onset date [mandatory], and end date [if available])
- fatal adverse events (SAEs) (onset date (mandatory), and end date (if available))
- Pregnancy record
- Originals or copies of laboratory results or examinations (in validated electronic format, if available)
- Conclusion of Patient's Participation in the study

The physician must keep the original informed consent form signed by the patient (a signed copy is given to the patient).

The investigator should maintain a list of appropriately qualified persons to whom he/she has delegated trial duties. All persons authorized to make entries and/or corrections on CRFs will be included on the Authority Form.

No information in source documents about the identity of the patients will be disclosed. No study document should be destroyed without prior written agreement between Boehringer Ingelheim and the investigator. Should the investigator wish to assign the study records to another party or move them to another location, he/she must notify Boehringer Ingelheim in advance.

9.10.2.2 Direct access to source data and documents

The investigator/institution will permit study-related monitoring, audits, IRB/IEC review and regulatory inspection, providing direct access to all related source data/documents. CRFs and all source documents, including progress notes, copies of laboratory, and medical test results, must be available at all times for review by the sponsor's clinical study monitor, auditor, and inspection by health authorities (e.g. US Food and Drug Administration [FDA]). The Clinical Research Associate (CRA)/Clinical Monitor Local (CML) and the auditor may review all CRFs and written informed consents. The accuracy of the data will be verified by reviewing the documents described in Section 9.10.2.1.

10. PROTECTION OF HUMAN SUBJECTS

The study will be carried out in compliance with the protocol, the principles laid down in the Declaration of Helsinki, in accordance with the ICH Harmonized Tripartite Guideline for Good Clinical Practice (GCP) (to the extent applicable to the NIS setting and required by local regulations), Good Epidemiological Practice (GEP), Guidelines for Good Pharmacoepidemiology Practice (GPP), and relevant BI Standard Operating Procedures (SOPs). Standard medical care (prophylactic, diagnostic and therapeutic procedures) remains in the responsibility of the treating physician of the patient.

The investigator should inform the sponsor immediately of any urgent safety measures taken to protect the study subjects against any immediate hazard, and also of any serious breaches of the protocol/ICH GCP.

The rights of the investigator and of the sponsor with regard to publication of the results of this study are described in the investigator contract. As a general rule, no study results should be published prior to finalization of the Study Report and consent from sponsor.

Insurance Cover: The requirements for insurance depend on local law and legislations. If required, the terms and conditions of the insurance cover are made available to the investigator and the patients, and the documentation must be archived in the Investigator Site File (ISF).

10.1 STUDY APPROVAL, PATIENT INFORMATION, AND INFORMED CONSENT

This study will be initiated only after all required legal documentation has been reviewed and approved by the respective Institutional Review Board (IRB)/Independent Ethics Committee (IEC) and Competent Authority (CA) according to national and international regulations. The same applies to the implementation of changes introduced by amendments.

Prior to patient participation in the study, written informed consent must be obtained from each patient (or the patient's legally accepted representative) according to ICH GCP and to the regulatory and legal requirements of the participating country. Each signature must be personally dated by each signatory and the informed consent and any additional patient-information form retained by the investigator as part of the study records. A signed copy of the informed consent and any additional patient information must be given to each patient or the patient's legally accepted representative.

The patient must be informed that his/her personal study-related data will be used by Boehringer Ingelheim in accordance with the local data protection law. The level of disclosure must also be explained to the patient. Eligible patients may only be included in the study after providing written (witnessed, where required by law or regulation), IRB/EC-approved informed consent, or, if incapable of doing so, after such consent has been provided by a legally acceptable representative of the patient. In cases where the patient's representative gives consent, the patient should be informed about the study to the extent possible given his/her understanding. If the patient is capable of doing so, he/she should assent by personally signing and dating the written informed consent document or a separate

assent form. Informed consent must be obtained before any data are collected. The process of obtaining informed consent should be documented in the patient source documents.

The patient must be informed that his/her medical records may be examined by authorized monitors (CML/CRA) or Quality Medicine auditors appointed by Boehringer Ingelheim, by appropriate IRB/IEC members, and by inspectors from regulatory authorities.

10.2 STATEMENT OF CONFIDENTIALITY

Individual patient medical information obtained as a result of this study is considered confidential and disclosure to third parties is prohibited with the exceptions noted below. Patient confidentiality will be ensured by using patient identification code numbers.

No subject names will be supplied to Boehringer Ingelheim or other responsible parties. Only the subject number and subject initials will be recorded on the CRF, and if the subject's name appears on any other document (e.g., laboratory report), it must be obliterated before a copy of the document is supplied to Boehringer Ingelheim or other responsible parties. Study findings stored on a computer will be stored in accordance with local data protection laws.

The investigator will maintain a personal subject identification list (subject numbers with the corresponding subject names) to enable records to be identified.

Treatment data may be given to the patient's personal physician or to other appropriate medical personnel responsible for the patient's welfare. Data generated as a result of the study need to be available for inspection on request by the participating physicians, the sponsor's representatives, by the IRB / IEC and the regulatory authorities. All personal information made available for inspection will be handled in strictest confidence and in accordance with local data protection laws.

11. MANAGEMENT AND REPORTING OF ADVERSE EVENTS/ADVERSE REACTIONS

11.1 DEFINITIONS OF ADVERSE EVENTS

Adverse event

An adverse event (AE) is defined as any untoward medical occurrence in a patient or clinical investigation subject administered a medicinal product and which does not necessarily have a causal relationship with this treatment. An adverse event can, therefore, be any unfavorable and unintended sign (e.g. an abnormal laboratory finding), symptom, or disease temporally associated with the use of a medicinal product, whether or not considered related to the medicinal product.

Adverse reaction

An adverse reaction is defined as a response to a medicinal product which is noxious and unintended. The response in this context means that a causal relationship between a medicinal product and an adverse event is at least a reasonable possibility. Adverse reactions may arise from the use of the product within or outside the terms of the marketing authorization or from occupational exposure. Conditions of use outside the marketing authorization include off-label use, overdose, misuse, abuse and medication errors.

Serious adverse event

A serious adverse event is defined as any AE which

- results in death,
- is life-threatening,
- requires in-patient hospitalization, or
- prolongation of existing hospitalization,
- results in persistent or significant disability or incapacity, or
- is a congenital anomaly/birth defect

Life-threatening in this context refers to a reaction in which the patient was at risk of death at the time of the reaction; it does not refer to a reaction that hypothetically might have caused death if more severe.

Medical and scientific judgment should be exercised in deciding whether other situations should be considered serious reactions, such as important medical events that might not be immediately life-threatening or result in death or hospitalization but might jeopardize the patient or might require intervention to prevent one of the other outcomes listed above. Examples of such events are intensive treatment in an emergency room or at home for allergic bronchospasm, blood dyscrasias or convulsions that do not result in hospitalization

or development of dependency or abuse. Any suspected transmission via a medicinal product of an infectious agent is also considered a serious adverse reaction.

Adverse event of special interest (AESI)

The term Adverse Event of Special Interest (AESI) relates to any specific AE that has been identified at the project level as being of particular concern for prospective safety monitoring and safety assessment within this study, e.g. the potential for AEs based on knowledge from other compounds in the same class.

No AESIs have been defined for this study.

11.2 ADVERSE EVENT AND SERIOUS ADVERSE EVENT COLLECTION AND REPORTING

The investigator shall maintain and keep detailed records of all AEs in their patient files.

Collection of AEs

The study design is of non-interventional nature and the study is conducted within the conditions of the approved marketing authorization. Sufficient data from controlled interventional trials are available to support the evidence on the safety and efficacy of the studied BI drug. For this reason, the following AE collection and reporting requirements have been defined.

The following must be collected by the investigator in the CRF from signing the informed consent onwards until the end of the study:

- All adverse drug reaction (ADRs) (serious and non-serious),
- All AEs with fatal outcome,

All ADRs, including those persisting after study completion must be followed up until they are resolved, have been sufficiently characterized, or no further information can be obtained.

The investigator should carefully assess whether an AE constitutes an ADR using the information below.

Causal relationship of adverse event

The definition of an adverse reaction implies at least a reasonable possibility of a causal relationship between a suspected medicinal product and an adverse event. An adverse reaction, in contrast to an adverse event, is characterized by the fact that a causal relationship between a medicinal product and an occurrence is suspected.

Medical judgment should be used to determine the relationship, considering all relevant factors, including the pattern of reaction, temporal relationship, de-challenge or re-challenge, and confounding factors such as concomitant medication, concomitant diseases, and relevant history.

Arguments that may suggest a **reasonable causal relationship** could be:

- The event is **consistent with the known pharmacology** of the drug
- The event is known to be caused by or **attributed to the drug class**.
- A **plausible time to onset of the event** relative to the time of drug exposure.
- Evidence that the **event is reproducible** when the drug is re-introduced
- **No medically sound alternative etiologies** that could explain the event (e.g. preexisting or concomitant diseases, or co-medications).
- The event is typically **drug-related and infrequent in the general population** not exposed to drugs (e.g. Stevens-Johnson syndrome).
- An indication of dose-response (i.e. greater effect size if the dose is increased, smaller effect size if the dose is diminished).

Arguments that may suggest that there is **no reasonable possibility of a causal relationship** could be:

- No plausible time to onset of the event relative to the time of drug exposure is evident (e.g. pre-treatment cases, diagnosis of cancer or chronic disease within days/weeks of drug administration; an allergic reaction weeks after discontinuation of the drug concerned)
- Continuation of the event despite the withdrawal of the medication, taking into account the pharmacological properties of the compound (e.g. after 5 half-lives).
- Of note, this criterion may not be applicable to events whose time course is prolonged despite removing the original trigger.
- Additional arguments amongst those stated before, like alternative explanation (e.g. situations where other drugs or underlying diseases appear to provide a more likely explanation for the observed event than the drug concerned).
- Disappearance of the event even though the study drug treatment continues or remains unchanged.

Intensity of adverse event

The intensity of the AE should be judged based on the following:

- Mild: Awareness of sign(s) or symptom(s) which is/are easily tolerated
- Moderate: Enough discomfort to cause interference with usual activity
- Severe: Incapacitating or causing inability to work or to perform usual activities

Pregnancy:

In rare cases, pregnancy might occur in a study. Once a subject has been enrolled into the study, after having taken Pradaxa®, the investigator must report any drug exposure during pregnancy, which occurred in a female subject or in a partner to a male subject to the Sponsor by means of Part A of the Pregnancy Monitoring Form. The outcome of the

pregnancy associated with the drug exposure during pregnancy must be followed up and reported by means of Part B of the Pregnancy Monitoring Form.

In the absence of a reportable AE, only the Pregnancy Monitoring Form must be completed, otherwise, the NIS AE form is to be completed and forwarded as well within the respective timelines.

Expedited Reporting of AEs and Drug Exposure During Pregnancy

The following must be reported by the investigator on the NIS AE form from signing the informed consent onwards until the end of the study:

Type of Report	Timeline
All serious ADRs associated with Pradaxa®	immediately within 24 hours
All AEs with fatal outcome in patients exposed to Pradaxa®	immediately within 24 hours
All non-serious ADRs associated with Pradaxa®	7 calendar days
All pregnancy monitoring forms	7 calendar days

The same timelines apply if follow-up information becomes available for the respective events. In specific occasions, the Investigator could inform the Sponsor upfront via telephone. This does not replace the requirement to complete and fax the NIS AE form.

Information required

For each reportable adverse event, the investigator should provide the information requested on the appropriate CRF pages and the NIS AE form.

Reporting of related Adverse Events associated with any other BI drug

The investigator is encouraged to report all adverse events related to any BI drug other than Pradaxa® according to the local regulatory requirements for spontaneous AE reporting at the investigator's discretion by using the locally established routes and AE report forms. The term AE includes drug exposure during pregnancy, and, regardless of whether an AE occurred or not, any abuse, off-label use, misuse, medication error, occupational exposure, lack of effect, and unexpected benefit.

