- Conduct safety reporting for Pradaxa[®] relevant adverse drug reaction (serious, non-serious), fatal AEs, and pregnancies; and record them on corresponding ADR forms and CRF pages.
- Complete the screening log for all patients that do not qualify at baseline*.
- Complete required CRFs.

[#]Information to be collected, whenever available, for CHA₂DS₂-VASC score and HAS-BLED score calculation

Age, gender, and part of concomitant diseases/comorbidities, risk factors, medical history, concomitant therapies, and lab assessments will be collected for the CHA₂DS₂-VASC score and HAS-BLED score calculation, **if available**. The data time frame on medical chart is defined as below:

- Demographics (age and gender): at the baseline visit.
- Comorbidities, risk factors, medical history, and concomitant therapies: prior to enrolment.

- Lab assessment: the most updated data conducted prior to enrolment, if regular practice available.

The description of scoring CHA₂DS₂-VASc and HAS-BLED is summarized in Section 9.3.4.

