****Information to be collected on screening failures***

The screening log entry with demographic information and the primary reason for not continuing or ineligibility must be completed for all screened patients that do not qualify for baseline visit (Visit 1). No CRF other than the screening log will be collected for these patients. The subject number of these ineligible patients should be kept, and the following enrolments will be numbered in sequence.

Initiation period (Visit 2):

During a routine practice visit occurring at 30 to 45 days after baseline, the following assessments will be documented, **if available**:

- Weight will be recorded to calculate creatinine clearance (CrCl).
- New or changed concomitant diseases/comorbidities.
- Changes in concomitant therapies.
- Collection of serum creatinine, if available, to calculate creatinine clearance (CrCl). Serum creatinine assessed within 30 to 45 days after enrolment will be collected. CrCl will be calculated according to Cockcroft-Gault formula (using weight collected at Visit 2 and serum creatinine assessed within 30 to 45 days after enrolment).
- Collect dosing of Pradaxa® and reasons for dose change (if applicable).
- Patients will be asked to complete the PACT-Q2 questionnaire.
- Reasons for Pradaxa® or VKA discontinuation (if applicable).
- Conduct safety reporting for Pradaxa® relevant ADR (serious, non-serious), fatal AEs, and pregnancies; and record them on corresponding ADR forms and CRF pages.
- Complete required CRFs.

Continuation period (Visit 3):

During a routine practice visit occurring at 150 to 210 days after baseline, the following assessments will be documented, **if available**:

- Weight will be recorded to calculate creatinine clearance (CrCl).
- New or changed concomitant diseases/comorbidities.
- Changes in concomitant therapies.
- Collection of serum creatinine, if available, to calculate creatinine clearance (CrCl). Serum creatinine assessed within 150 to 210 days after enrolment will be collected. CrCl will be calculated according to Cockcroft-Gault formula (using weight collected at Visit 3 and serum creatinine assessed within 150 to 210 days after enrolment).
- Collect dosing of Pradaxa® and reasons for dose change (if applicable).
- Patients will be asked to complete the PACT-Q2 questionnaire.

Proprietary confidential information © 2017 Boehringer Ingelheim International GmbH or one or more of its affiliated companies

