9.7.3 Safety analysis

Safety analyses will be performed separately for Cohort A and Cohort B, and will include all enrolled patients with an actual follow-up. Statistical analysis and reporting of AEs (i.e. Pradaxa® relevant ADR (serious and non-serious), fatal AEs, and pregnancies) will be descriptive in nature and based on BI standards. No hypothesis testing is planned. The assessment of safety will be based mainly on the frequency of adverse events, which includes

all serious adverse events. All adverse events will be summarized with the coding term, severity, and relationship to study drug by frequency tables with the counts and percentage.

In addition, occurrences of Pradaxa® relevant ADRs will be analyzed relative to the number of patients treated as well as observed person-years (i.e. time at risk). If no concurrent Pradaxa® treatment is administered, then events occurring within a washout period of 3 days after discontinuation of Pradaxa® treatment will be assigned to the last treatment given. This washout period will also be included as time at risk for derivation of total person-years. ADRs that deteriorate under treatment will also be considered as “treatment emergent”. Events occurring prior to first intake of Pradaxa® treatment prescribed at baseline, during periods without Pradaxa® treatment (excluding washout periods), or after the end of the 6-month follow-up (excluding washout periods) will not be considered treatment emergent events, and will not be included in the summary tables.

Furthermore, serious adverse events will be listed with event narration. Adverse events will be coded using the latest version of Medical dictionary for regulatory activities (MedDRA) terminology.

The following parameters will be included in the safety analyses:

- Adverse drug reactions
- Adverse drug reactions leading to discontinuation of anticoagulation treatment
- Serious adverse drug reactions
- Adverse events leading to deaths

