## 10.4 Safety Endpoints

- AEs (i.e. Pradaxa® relevant ADR (serious and non-serious), fatal AEs, and pregnancies)

Safety analyses will be performed separately for Cohort A and Cohort B.

The following parameters will be included in the safety analyses:

- Adverse drug reactions
- Adverse drug reactions leading to discontinuation of anticoagulation treatment
- Serious adverse drug reactions
- Adverse events leading to deaths

DRAFT

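### Protocol 11.2 collects all ADRs but the visit schedule and safety endpoint cover only Pradaxa-relevant ones, so capture of VKA ADRs is undefined and a pooled Cohort B ADR percentage would be diluted

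*Protocol*

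**What the plan says.** **Collection rule, Protocol 11.2.** The list is introduced by "The following must be collected by the investigator in the CRF from signing the informed consent onwards until the end of the study". Its first item is "All adverse drug reaction (ADRs) (serious and non-serious"), and its second is AEs with a fatal outcome. Neither names a drug. Protocol 11.1 is equally general: "An adverse reaction is defined as a response to a medicinal product which is noxious and unintended". Just before the list, 11.2 justifies limited collection thus: "Sufficient data from controlled interventional trials are available to support the evidence on the safety and efficacy of the studied BI drug". The expedited-reporting table later in 11.2 is expressly limited to Pradaxa.

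**Visit schedule, Protocol 9.2.3.** The Visit 2 instruction is "Conduct safety reporting for Pradaxa® relevant ADR (serious, non-serious), fatal AEs, and pregnancies". Visits 1 and 3 have the same scope. Footnote 10 of Protocol Table 1 and of SAP Table 7.1 repeats it.

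**Analysis.** Protocol 9.7.3 and SAP 6.2.3 and 10.4 define the analysed events as "Pradaxa® relevant ADR (serious and non-serious), fatal AEs, and pregnancies". The parameter list in 9.7.3 and SAP 10.4 then uses unqualified terms, including "Adverse drug reactions leading to discontinuation of anticoagulation treatment". The safety population (SAP 8.3) is all enrolled patients with follow-up, and results are given separately for Cohorts A and B. No split of Cohort B by drug is stated. Protocol 9.7.3 and SAP 11.5 keep events in periods without Pradaxa, apart from a 3-day washout, out of the summary tables.

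**The concern.** Two instructions for the same CRF have different scopes. Take a VKA initiator with a bleed that the investigator attributes to the VKA. Section 11.2, read as written, asks for it; the visit list does not. The documents do not say which governs, so the recorded fraction of VKA ADRs could lie anywhere between none and all.

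Uneven capture could also pass unnoticed. Source data verification is 20% (Protocol 9.8), and SAP 9.2 defines no protocol violations or deviations.

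A second problem remains even if everyone reads the plan as Pradaxa-only. The VKA initiators stay in the Cohort B safety population but can contribute no countable ADR while on VKA. A percentage for Cohort B as a whole then describes neither drug.

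**Working it through.** The documents give no ADR rate and no safety-based sample size, so there is no stated figure to reproduce. The planned counts do add up: 300 + 500 + 200 = 1000.

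**Step 1. Follow a VKA-attributed ADR in a VKA initiator through each rule.**

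| Place | Is it covered? |
|---|---|
| Protocol 11.2, CRF collection list | Yes, as worded |
| Protocol 9.2.3, Visits 1 to 3 | No |
| Footnote 10, Protocol Table 1 and SAP Table 7.1 | No |
| Protocol 11.2, expedited reporting | No |
| Endpoint definition, Protocol 9.7.3, SAP 6.2.3 and 10.4 | No |
| Parameter list, Protocol 9.7.3 and SAP 10.4 | Not qualified by drug |
| Summary tables, Protocol 9.7.3 and SAP 11.5 | Excluded (no Pradaxa treatment) |

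**Step 2. Does the difference between CRF collection and expedited reporting explain this?** No. The Visit 1 instruction covers "relevant adverse drug reaction (serious, non-serious), fatal AEs, and pregnancies; and record them on corresponding ADR forms and CRF pages". The visit lists therefore govern CRF recording too, and they conflict with 11.2 on the same form.

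**Step 3. Effect on a Cohort B percentage.** Inputs: 500 Pradaxa and 200 VKA initiators (Protocol 9.5, SAP 7.4), so VKA initiators are 200/700 = 28.6% of planned Cohort B. Let p be the ADR proportion, assumed equal in both groups for illustration, and c the share of VKA ADRs that are recorded and counted.

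Pooled Cohort B proportion = (500p + 200pc)/700

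| Assumed p | c = 0 | c = 0.5 | c = 1 |
|---|---|---|---|
| 5% | 3.6% | 4.3% | 5.0% |
| 10% | 7.1% | 8.6% | 10.0% |
| 20% | 14.3% | 17.1% | 20.0% |

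Example: p = 10%, c = 0 gives 50/700 = 7.1%. The apparent proportion among VKA initiators alone is pc: 0%, 5% or 10% at p = 10%. The Pradaxa-initiator proportion does not depend on c.

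**Step 4. Which column applies?** If the summary-table rule is applied as written, VKA-period events are excluded whether or not a site recorded them, so c = 0 in those tables. The pooled figure is then 500p/700 = 0.714p for any p. The intermediate columns matter only for output produced outside that rule, such as a listing, or a table built from the unqualified parameter names.

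**The case against.** The strongest defence is that the plan is Pradaxa-only and 11.2 has one loosely worded bullet. The bullet follows a rationale about the sponsor's own drug. Section 11.2 ties CRF pages to reportable events, and the reportable ADRs are Pradaxa ones. The visit lists agree at all three visits, and SAP 10.4 opens with a Pradaxa-only definition before its parameter list. Physicians are trained on safety reporting (Protocol 9.8), and the CRF, which is not in the documents, may settle the matter. Safety is descriptive, with no hypothesis test.

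Much of this stands, and it rules out three stronger readings that a reader might infer:

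- **That 11.2 orders all ADRs recorded for every patient.** It does not say so. That is an inference from an unqualified item whose context allows a Pradaxa-only reading.
- **That VKA ADRs will be captured site by site.** The documents permit uneven capture but do not show it.
- **That Cohort B ADR results cannot be read, or that the tables will show a spurious safety difference.** Pradaxa ADRs in Pradaxa initiators and fatal AEs are required under both wordings. VKA-period events are excluded from the summary tables, and no safety comparison between the drugs is planned.

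The defence does not remove the conflict. Section 11.2 names Pradaxa where it restricts expedited reporting and omits it from the collection list, so the wider reading is a natural one. Nor does a Pradaxa-only reading settle the denominator: SAP 11.5 relates ADRs to patients treated without saying with which drug.

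**Conclusion.** The inconsistency is real, and its consequence is limited. Whether VKA-attributed ADRs in about 200 planned VKA initiators belong in the CRF is undefined. Three quantities are unsafe to report: a VKA ADR rate, an informal VKA versus Pradaxa contrast, and any ADR percentage pooled over Cohort B. Pradaxa ADRs in Pradaxa initiators are unaffected, as are the PACT-Q outcomes.

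The one size that needs no assumed ADR rate is the dilution: a pooled Cohort B percentage would be about 0.71 of the Pradaxa proportion. This rests on the planned 500:200 split, on all 700 patients forming the denominator, and on VKA initiators contributing no countable ADR. The percentages in the table are illustrations over an assumed 5% to 20%.

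**What to change.** Use one scope throughout.

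**Option 1, Pradaxa only.**
- Limit the ADR item in Protocol 11.2 and the parameters in Protocol 9.7.3 and SAP 10.4, including ADRs leading to discontinuation, to Pradaxa-relevant ADRs.
- Use Pradaxa-treated patients as the denominator of every ADR table, and name it in the table.
- Show Cohort B safety by drug, and say where fatal AEs in VKA initiators appear, since they are collected under both wordings.
- State that no ADR result is reported for VKA initiators.

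This costs wording only. The SAP part can still be done in a SAP marked as a draft, even if data collection has closed. The price is a narrower safety statement.

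**Option 2, if the sponsor wants VKA ADRs recorded.** Change together the visit lists, footnote 10 in both documents, the endpoint definition in Protocol 9.7.3 and SAP 6.2.3 and 10.4, and the treatment-emergent and person-time rules in Protocol 9.7.3 and SAP 11.5. Widening collection alone would not work, because those last rules would still exclude the added events from the summary tables. This option also adds CRF entries for about 200 patients.
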